2 INTRODUCTION

Merck Sharp & Dohme Corp. (MSD) is developing an investigational 15-valent pneumococcal conjugate vaccine (PCV) (referred to as V114) for the prevention of pneumococcal disease caused by the serotypes in the vaccine. V114 contains the 13 serotypes (1, 3, 4, 5, 6A, 6B, 7F, 9V, 14, 18C, 19A, 19F, 23F) present in the licensed vaccine Prevnar 13™ (pneumococcal 13-valent conjugate vaccine [diphtheria CRM₁₉₇ protein], Wyeth Pharmaceuticals, a subsidiary of Pfizer, Inc., Philadelphia, PA), plus 2 additional serotypes (22F, 33F).

2.1 Study Rationale

Allogeneic hematopoietic stem cell transplant (allo-HSCT) recipients are at increased risk for pneumococcal infections and have a high risk for invasive pneumococcal disease (IPD) [Engelhard, D., et al 2002] [Giebink, G. S., et al 1986] [Youssef, S., et al 2007]. IPD is associated with high morbidity and mortality in allo-HSCT recipients, with rates of disease being 20- to 30-fold higher than the general population. Pneumococcal disease can occur early (<3 months post-transplantation), but the majority of IPD cases are reported ≥4 months post transplantation [Engelhard, D., et al 2002].

Immunization is the main preventative strategy against pneumococcal disease [Rubin, L. G., et al 2014]. The majority of pneumococcal disease cases are observed >4 months after HSCT [Engelhard, D., et al 2002] [Cordonnier, C., et al 2009]. The vaccination series is recommended to be initiated at 3 to 6 months post-transplantation to ensure earlier protection against *Streptococcus pneumoniae* [Rubin, L. G., et al 2014]. Several clinical studies in both adult and pediatric populations have demonstrated the acceptable safety and immunogenicity profiles of 3 to 4 doses of PCV given 1 month apart followed by a dose of PNEUMOVAX™23 [Cordonnier, C., et al 2015]. Current international guidelines recommend the administration of 3 doses of PCV (eg, Prevnar 13™), at 1-month intervals, to be started from 3 to 6 months after transplant, followed at 12 months after transplant by a dose of PNEUMOVAX™23 (pneumococcal vaccine, polyvalent [23-valent]) [Tomblin, Marcie, et al 2009] [Rubin, L. G., et al 2014]. In patients with chronic graft-versus-host disease (GVHD), an additional dose of PCV can be administered at 12 months after HSCT [Rubin, L. G., et al 2014], instead of PNEUMOVAX™23.

This clinical study is designed to describe the safety, tolerability, and immunogenicity of V114 compared with Prevnar 13™ in allo-HSCT recipients (≥3 years of age) who have not received a pneumococcal vaccine (vaccine-naïve) after the transplant. This study will also describe the safety and tolerability of PNEUMOVAX™23 administered 12 months after the allo-HSCT. Immune responses to the 15 serotypes contained in V114 following PNEUMOVAX™23 administration will also be described. Consistent with current guidelines, participants with chronic GVHD will receive a 4th dose of either V114 or Prevnar 13™ at 12 months post-transplant instead of PNEUMOVAX™23. Chronic GVHD should be assessed in accordance with NIH consensus criteria [Jagasia, M. H., et al 2015]. Recommendation for minimum platelet count is based on the Clinical Practice Guideline from the AABB [Kaufman, R. M., et al 2015]. Safety, tolerability, and immunogenicity

following administration of the 4th dose of either V114 or Prevnar 13™ will be described. The data from this study will contribute to the overall safety database and immunogenicity profile of V114 in individuals ≥ 3 years of age and older.

2.2 Background

2.2.1 V114 and Pneumococcal Disease

Refer to the Investigator's Brochure (IB) for V114 for more detailed background, including information on pneumococcal disease burden.

S. pneumoniae is a significant cause of disease worldwide, with clinical manifestations including pneumonia, meningitis, otitis media, sinusitis, and sepsis. Adults with comorbid conditions, in particular immunocompromised individuals, have a higher incidence of invasive pneumococcal disease (IPD) morbidity and mortality in all age groups compared to adults without the comorbid conditions [Lexau, C. A., et al 2005].

Currently licensed pneumococcal conjugate vaccines (eg, Prevnar™, Synflorix™, and Prevnar 13™) were first implemented in infant immunization programs in many countries worldwide. Prevnar™ was first licensed in 2000 and later replaced by Prevnar 13™ in 2009 for the European Union and in 2010 for the United States. Although Prevnar 13™ is indicated for children and adults, Synflorix™ is only indicated for children up to 5 years of age. Widespread use of PCVs has reduced the burden of pneumococcal disease caused by the serotypes contained in the vaccines in children who were targeted by the vaccination programs and unvaccinated individuals from other age groups (herd protection) [Centers for Disease Control and Prevention 2008] [Ruckinger, S., et al 2009] [Farrell, D. J., et al 2007] [Pilishvili, Tamara, et al 2010] [Lexau, C. A., et al 2005] [Metlay, J. P., et al 2006] [Whitney, Cynthia G., et al 2003] [Moore, M. R., et al 2015] [Lepoutre, A., et al 2015] [Weiss, S., et al 2015] [Martinelli, D., et al 2014] [Guevara, M., et al 2016] [Waight, P. A., et al 2015] [Jokinen, J., et al 2015] [Palmu, A. A., et al 2015] [Wagenvoort, G. H., et al 2016]. Prevnar 13™ was also shown to be efficacious against vaccine-type nonbacteremic pneumococcal pneumonia and IPD in adults ≥ 65 years of age [Bonten, M. J., et al 2015]. These study results were the basis of the recommendation from the ACIP for the sequential administration of Prevnar 13™ followed at least 12 months later by PNEUMOVAX™23 in adults ≥ 65 years of age [Tomczyk, S., et al 2014] [Kobayashi, M., et al 2015].

Although cases of IPD have decreased following implementation of PCVs, an increase in IPD caused by serotypes not covered by currently available vaccines has been observed. V114 contains 2 additional serotypes (22F, 33F) compared with Prevnar 13™. The selection of 22F and 33F was primarily based on epidemiological importance of these 2 additional serotypes. Recent data from the United States suggest that 22F is the most common serotype not included in Prevnar 13™ in adults ≥ 18 years of age, causing 13% of IPD cases. Serotype 33F is associated with an additional 5% of IPD cases [Moore, M. R., et al 2015]. Data from the United Kingdom also showed that, in 2013/2014, 22F and 33F are frequent serotypes in adults ≥ 65 years of age, accounting for approximately 10% and 4% of IPD cases in that age group, respectively [Waight, P. A., et al 2015]. Data from 2014 reported in the 2016 annual

epidemiological report on IPD by the European Centre for Disease Prevention and Control showed that both serotypes 22F and 33F are among the most common serotypes causing IPD [European Centre for Disease Prevention and Control 2016]. In pediatrics, approximately 4 years after inclusion of Prevnar™ in the United States infant immunization schedule, serotypes 22F and 33F accounted for approximately 13% of IPD cases in children <5 years of age (incidence rate of IPD due to 22F and 33F combined of 3.1 cases per 100,000 person-years [PY]), in contrast to 1.3% of IPD cases in the pre-PCV7 era (incidence rate of 22F and 33F IPD of 1.2 cases per 100,000 PY) [Hicks, L. A., et al 2007]. By 2013, both 22F and 33F were among the leading serotypes causing IPD beyond those already included in Prevnar 13™, accounting for approximately 21% of all IPD in children <5 years of age in the United States [Moore, M. R., et al 2015]

The serotypes included in V114 will provide broad coverage of the leading serotypes associated with pneumococcal disease worldwide. V114 is designed to meet continuing medical and public health needs for PCVs globally, as well as to address the emergence of pneumococcal disease caused by serotypes not contained in currently licensed PCVs. V114 is designed to offer broader serotype coverage than Prevnar 13™ against pneumococcal disease in both pediatric and adult populations.

2.2.2 Preclinical and Clinical Studies

Refer to the IB for information on completed preclinical and clinical studies conducted with V114.

2.2.3 Information on Other Study-related Therapy

2.2.3.1 Prevnar 13™

Refer to approved labeling for detailed background information on Prevnar 13™.

Prevnar 13™ contains all of the pneumococcal serotypes included in Prevnar™ (4, 6B, 9V, 14, 18C, 19F, and 23F) plus 6 additional serotypes (1, 3, 5, 6A, 7F, and 19A). The adult indication was approved based on immune responses elicited by Prevnar 13™ in comparison with PNEUMOVAX™23. A placebo-controlled clinical efficacy study (Community Acquired Pneumonia Immunization Trial in Adults [CAPiTA]) evaluated the efficacy of Prevnar 13™ against pneumococcal pneumonia and IPD in immunocompetent adults ≥65 years of age. Results from CAPiTA showed that Prevnar 13™ was 45.6% (95% confidence interval [CI]: 21.8% to 62.5%) efficacious against vaccine-type nonbacteremic pneumococcal pneumonia and 75.0% (95% CI: 41.4% to 90.8%) efficacious against vaccine-type IPD in adults ≥65 years of age [Bonten, M. J., et al 2015].

In many countries, Prevnar 13™ is given as a part of routine immunization schedules for all infants and children 2 to 59 months of age and for children 60 to 71 months of age with immunocompromising conditions. Children without a history of immunization with Prevnar 13™ are recommended to receive catch up immunization with Prevnar 13™, regardless of previous immunization with other PCVs containing fewer PnPs serotypes. The Advisory Committee on Immunization Practices (ACIP) also recommends children 6 to

18 years of age with immunocompromising conditions, functional or anatomic asplenia, CSF leaks, or cochlear implants, also receive Prevnar 13™. Children and adults who have undergone stem cell transplantation receive 3 dose series of Prevnar 13™ after transplantation [Centers for Disease Control and Prevention (CDC) 2013].

Prevnar™ and Prevnar 13™ are also known as Prevenar™ and Prevenar 13™ in many countries outside of the United States; these vaccines are referred to as Prevnar™ and Prevnar 13™ throughout this document.

2.2.3.2 PNEUMOVAX™23

Refer to approved labeling for detailed background information on PNEUMOVAX™23.

PNEUMOVAX™23 is comprised of the polysaccharides from 23 of the most important serotypes causing disease in adults (1, 2, 3, 4, 5, 6B, 7F, 8, 9N, 9V, 10A, 11A, 12F, 14, 15B, 17F, 18C, 19A, 19F, 20, 22F, 23F, and 33F). The formulation is not adjuvanted and no carrier protein is used.

In the United States, PNEUMOVAX™23 is recommended by the ACIP for routine use in immunocompetent adults ≥ 65 years of age as sequential administration at least 1 year after Prevnar 13™ [Kobayashi, M., et al 2015]. It is also recommended for use in adults aged 19 to 64 years of age with underlying medical conditions that increase the risk for serious pneumococcal infection. These conditions include but are not limited to chronic heart disease, chronic lung disease (including chronic obstructive pulmonary disease, emphysema, and asthma), diabetes mellitus, alcoholism, chronic liver disease (including cirrhosis), and cigarette smoking [Centers for Disease Control and Prevention 2010].

PNEUMOVAX™23 is also recommended in immunocompromised adults ≥ 19 years of age; in this population, a dose of PNEUMOVAX™23 is recommended ≥ 8 weeks following a dose of Prevnar 13™ [Kobayashi, M., et al 2015]. Vaccination with PNEUMOVAX™23 is also recommended for children 2 to 18 years of age with underlying medical conditions after completing all recommended Prevnar 13™ doses [Centers for Disease Control and Prevention (CDC) 2013]. Many countries follow similar age-based and/or risk-based recommendations for the use of PNEUMOVAX™23 [Castiglia P. 2014].

2.3 Benefit/Risk Assessment

It cannot be guaranteed that participants in clinical studies will directly benefit from intervention during participation, as clinical studies are designed to provide information about the safety and effectiveness of an investigational vaccine.

Approximately 50% of participants will receive Prevnar 13™, the standard of care, as the active comparator in this study. Based on the available data, V114 is expected to provide comparable immune responses to Prevnar 13™ for the shared serotypes while providing additional coverage for the 2 serotypes (22F, 33F) unique to V114. However, it is unknown if the investigational V114 will have the same benefit as Prevnar 13™ in the recipients of allo-HSCT.

As per current guidelines, eligible participants will also receive PNEUMOVAX™23 at 12 months after allo-HSCT to enhance immune responses and broaden protection against additional serotypes [Rubin, L. G., et al 2014]. However, participants who develop chronic GVHD during their first year after allo-HSCT will be considered ineligible to receive PNEUMOVAX™23. Instead of PNEUMOVAX™23, participants with chronic GVHD will receive a 4th dose of blinded study vaccine (ie, V114 or Prevnar 13™) at 12 months after allo-HSCT.

Additional details regarding specific benefits and risks for participants participating in this clinical study may be found in the accompanying IB and Informed Consent Form (ICF). See Appendix 10.7.1 for Country-specific requirements for Sweden.

3 HYPOTHESIS, OBJECTIVES, AND ENDPOINTS

The following objectives and endpoints will be evaluated in adult and pediatric recipients of allogeneic hematopoietic stem cell transplant (allo-HSCT).

Objectives	Endpoints
Primary	

 Objective: To evaluate the safety and tolerability of 3 doses of V114 and 3 doses of Prevnar 13™ with respect to the proportion of participants with adverse events (AEs) within each vaccination group. 	
Following any of the 3 doses of V114 or Prevnar 13™ for adults ≥18 years of age:
 
 Solicited injection-site AEs from Day 1 through Day 5 postvaccination Solicited systemic AEs from Day 1 through Day 14 postvaccination Vaccine-related serious adverse events (SAEs) from Day 1 postvaccination to Month 12 after allo-HSCT 
Following any of the 3 doses of V114 or Prevnar 13™ for pediatrics (3 to <18 years of age):
 
 Solicited injection-site AEs from Day 1 through Day 14 postvaccination Solicited systemic AEs from Day 1 through Day 14 postvaccination Vaccine-related serious adverse events (SAEs) from Day 1 postvaccination to Month 12 after allo-HSCT

 Objective: To evaluate the serotype-specific immunoglobulin G (IgG) Geometric Mean Concentrations (GMCs) at 30 days following the 3rd dose of V114 and following the 3rd dose of Prevnar 13™ within each vaccination group. 	
 Serotype-specific IgG responses for the 15 serotypes in V114 at Day 90

Secondary
	

 Objective: To evaluate the safety and tolerability of PNEUMOVAX™23 (administered 12 months after allo-HSCT in participants who do not develop GVHD) with respect to the proportion of participants with AEs within each vaccination group. 	
Following vaccination with PNEUMOVAX™23 for adults ≥18 years of age:
 
 Solicited injection-site AEs from Day 1 through Day 5 postvaccination Solicited systemic AEs from Day 1 through Day 14 postvaccination Vaccine-related SAEs from Month 12 after allo- HSCT to 1 month after vaccination or the completion of the study. 
Following vaccination with PNEUMOVAX™23 for pediatrics (3 to <18 years of age):
 
 Solicited injection-site AEs from Day 1 through Day 14 postvaccination Solicited systemic AEs from Day 1 through Day 14 postvaccination Vaccine-related SAEs from Month 12 to after allo-HSCT to 1 month after vaccination or the completion of the study.

 Objective: To evaluate the safety and tolerability of a 4th dose of V114 and a 4th dose of Prevnar 13™ (both administered 12 months after allo-HSCT in participants who develop GVHD) with respect to the proportion of participants with AEs within each vaccination group. 	
Following vaccination with a 4th dose of V114 or Prevnar 13™ for adults ≥18 years of age:
 
 Solicited injection-site AEs from Day 1 through Day 5 postvaccination Solicited systemic AEs from Day 1 through Day 14 postvaccination Vaccine-related SAEs Day 1 through 6 months after 4th vaccination of V114 and Prevnar 13™ or completion of the study. 
Following vaccination with a 4th dose of V114 or Prevnar 13™ for pediatrics (3 to <18 years of age):
 
 Solicited injection-site AEs from Day 1 through Day 14 postvaccination Solicited systemic AEs from Day 1 through Day 14 postvaccination Vaccine-related SAEs from Day 1 through 6 months after 4th vaccination of V114 and Prevnar 13™ or completion of the study.

 Objective: To evaluate the serotype-specific opsonophagocytic activity (OPA) Geometric Mean Titers (GMTs) at 30 days following the 3rd dose of V114 and following the 3rd dose of Prevnar 13™ within each vaccination group. 	
 Serotype-specific OPA responses for the 15 serotypes in V114 at Day 90

 Objective: To evaluate the serotype-specific (1) OPA GMTs and IgG GMCs at baseline (prevaccination with V114 or Prevnar 13™) and (2) Geometric Mean Fold Rises (GMFRs) and proportions of participants with a ≥4-fold rise from baseline to 30 days following the 3rd dose of V114 and 3rd dose of Prevnar 13™ separately for both IgG and OPA responses within each vaccination group. 	
 Serotype-specific OPA and IgG responses for the 15 serotypes in V114 at Day 1 and Day 90

Exploratory	

 Objective: To evaluate the serotype-specific (1) IgG GMCs and OPA GMTs at 30 days postvaccination with either PNEUMOVAX™23 (participants without chronic GVHD) or a 4th dose of V114 or Prevnar 13™ (participants with chronic GVHD) administered at Month 12 after allo-HSCT within each vaccination group; (2) GMFRs and proportions of participants with a ≥4-fold rise from prevaccination (Month 12 after allo-HSCT) to 30 days following either PNEUMOVAX™23 or a 4th dose of V114 or Prevnar 13™ (Month 13 after allo-HSCT) for both IgG and OPA responses within each vaccination group. 	
 Serotype-specific IgG and OPA responses for the 15 serotypes in V114 at Month 12 and Month 13 after allo-HSCT

 Objective: To evaluate the serotype-specific IgG GMCs at 30 days postvaccination for participants administered 3 doses of V114 compared to participants administered 3 doses of Prevnar 13™. 	
 Serotype-specific IgG responses for the 15 serotypes in V114 at Day 90

4 STUDY DESIGN

4.1 Overall Design

This is a Phase 3, randomized, double-blind, active comparator-controlled, parallel-group, multicenter, clinical study to describe the safety, tolerability, and immunogenicity of V114 and Prevnar 13™ when administered as a 3-dose regimen in recipients of allo-HSCT.

Prospective participants will be screened for enrollment at Visit 1, which must occur within 30 days before Visit 2 (Day 1). At Visit 2 (Day 1), which must occur 90 to 180 days after a first allo-HSCT, eligible participants will be randomly assigned in a 1:1 ratio to 1 of the 2 blinded study vaccines (V114 or Prevnar 13™).

A total of approximately 250 adult and 50 pediatric participants will be randomized so that approximately 150 participants will receive V114 and approximately 150 participants will receive Prevnar 13™. The randomization process will be performed using stratification techniques to ensure a reasonable balance between the 2 study vaccine groups with regard to the following factors: use of systemic steroids within 14 days before randomization (Day 1),

age category (3 to <18 years and 18 to 49 years or ≥ 50 years), and haploidentical donor status (yes or no).

Blinded study vaccine (V114 or Prevnar 13™) will be administered to each eligible participant at each of the following 3 time points: Visit 2 (Day 1), Visit 3 (Day 30), and Visit 4 (Day 60).

Eligible participants will also receive a single dose of PNEUMOVAX™23 at Visit 6 (12 months after allo-HSCT). However, participants who develop chronic GVHD during the first year after allo-HSCT will be considered ineligible to receive PNEUMOVAX™23 and will instead receive a 4th dose of blinded study vaccine (V114 or Prevnar 13™) at Visit 6.

Participants will be followed for local and systemic AEs from Day 1 through Day 14 following each vaccination. Information for SAEs and deaths, regardless of whether the events are considered to be vaccine-related by the investigator, will be collected from the time consent is signed through completion of participation in the study. An external Data Monitoring Committee (DMC) will conduct a periodic review of safety and tolerability data for the adult V114 Phase 3 program. A description of the structure, function, and guidelines for decision-making by the DMC, along with the timing and content of the safety reviews will be outlined in the DMC charter. Information regarding the composition of the DMC is provided in Appendix 1.

Throughout a participant's participation in the study, new onset and/or change in GVHD as well as relapse and progression of underlying disease (ie, the disease for which allo-HSCT was performed) will be recorded as specific events of interest.

Blood samples for immunogenicity assays will be obtained at the following time points:

- Immediately before V114 or Prevnar 13™ vaccination at Visit 2 (Day 1)
- 30 days after the 3rd vaccination with V114 or Prevnar 13™ Visit 5 (Day 90)
- Immediately before vaccination with PNEUMOVAX™23, or 4th dose of either V114 or Prevnar 13™, administered 12 months after allo-HSCT (Visit 6)
- 30 days after vaccination with PNEUMOVAX™23, or 4th dose of either V114 or Prevnar 13™ (Visit 7)

After completion of electrochemiluminescence (ECL) and OPA testing, serum samples will be stored to conduct any additional study-related testing as required by regulatory agencies or the Sponsor. Leftover sera from the study may be used for the development and/or validation of pneumococcal assays after completion of all study-related immunogenicity testing; this applies only to sera received from randomized study participants who provided consent for future biomedical research.

Specific procedures to be performed during the study, as well as their prescribed times and associated visit windows, are outlined in the SoA in Section 1.3. Details of each procedure are provided in Section 8.

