^a PNEUMOVAX™23 is administered to participants who do not have chronic graft-versus-host disease. ^b For participants who have chronic graft-versus-host disease, a 4 th dose of V114 or Prevnar 13™ (double-blind; same as was administered for the first 3 doses) administered at Visit 6 (12 months after allo-HSCT) instead of PNEUMOVAX™23. allo-HSCT = allogeneic hematopoietic stem cell transplant; IB = Investigator’s Brochure; IM = intramuscular							
Total Number	2 intervention groups						
Duration of Participation	Each participant will participate in the study for approximately 11 months from the time the participant or the participant’s legally acceptable representative signs the Informed Consent Form (ICF) through the final contact.						

Study Governance Committees:

Steering Committee	No
Executive Oversight Committee	Yes
Data Monitoring Committee	Yes
Clinical Adjudication Committee	No
Study governance considerations are outlined in Appendix 1.	

Study Accepts Healthy Volunteers: No

A list of abbreviations used in this document can be found in Appendix 8.

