Visit Window:	Within 30 days before Visit 2	90 to 180 days after Allo-HSCT	Day 15 to Day 19 after Visit 2 ^a	Day 30 to Day 44 after Visit 2 ^a	Day 15 to Day 19 after Visit 3 ^b	Day 30 to Day 44 after Visit 3 ^b	Day 15 to Day 19 after Visit 4 ^c	Day 30 to Day 44 after Visit 4 ^c	Day 256 to Day 284 after Allo-HSCT	Day 335 to Day 395 after Allo-HSCT	Day 15 to Day 19 after Visit 6	Day 30 to Day 44 after Visit 6	Day 166 to Day 194 after Visit 6 ^d	
Screening Laboratory Tests	X													Complete blood count with differential, blood chemistry (including renal function).
Assignment of Randomization Number		X												
Participant Identification Card	X													
Prior/Concomitant Medication and Non-Study Vaccination Review		X	X	X	X	X	X	X		X	X	X		
V114 or Prevnar 13™ Administration (Blinded)		X		X		X								At each of the identified visits, participants will receive either a single dose of V114 or a single dose of Prevnar 13™.

Study Period	Screening	Intervention										Follow-up		Comments
Visit Number:	1	2	Phone Contact	3	Phone Contact	4	Phone Contact	5	Phone Contact	6	Phone Contact	7	Phone Contact ^d	
Scheduled Time:		Day 1	Day 15	Day 30	Day 45	Day 60	Day 75	Day 90	9 Months after Allo-HSCT	12 Months after Allo-HSCT	15 days after Visit 6	30 Days after Visit 6	6 Months after Visit 6	Results from all screening procedures at Visit 1 must be available before randomization into the study at Visit 2 (Day 1), which must occur ≤30 days after Visit 1.
Visit Window:	Within 30 days before Visit 2	90 to 180 days after Allo-HSCT	Day 15 to Day 19 after Visit 2 ^a	Day 30 to Day 44 after Visit 2 ^a	Day 15 to Day 19 after Visit 3 ^b	Day 30 to Day 44 after Visit 3 ^b	Day 15 to Day 19 after Visit 4 ^c	Day 30 to Day 44 after Visit 4 ^c	Day 256 to Day 284 after Allo-HSCT	Day 335 to Day 395 after Allo-HSCT	Day 15 to Day 19 after Visit 6	Day 30 to Day 44 after Visit 6	Day 166 to Day 194 after Visit 6 ^d	
PNEUMOVAX™23 Administration or V114 or Prevnar 13™ Administration (Blinded)										X				

Study Period	Screening	Intervention										Follow-up		Comments
Visit Number:	1	2	Phone Contact	3	Phone Contact	4	Phone Contact	5	Phone Contact	6	Phone Contact	7	Phone Contact ^d	

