Visit Window:	Within 30 days before Visit 2	90 to 180 days after Allo-HSCT	Day 15 to Day 19 after Visit 2 ^a	Day 30 to Day 44 after Visit 2 ^a	Day 15 to Day 19 after Visit 3 ^b	Day 30 to Day 44 after Visit 3 ^b	Day 15 to Day 19 after Visit 4 ^c	Day 30 to Day 44 after Visit 4 ^c	Day 256 to Day 284 after Allo-HSCT	Day 335 to Day 395 after Allo-HSCT	Day 15 to Day 19 after Visit 6	Day 30 to Day 44 after Visit 6	Day 166 to Day 194 after Visit 6 ^d	
Future Biomedical Research														
Blood (DNA) for Future Biomedical Research (Optional) for adult participants ≥18 years of age.		X												Collected from randomized participants who provided consent for future biomedical research (Section 8.8)
Saliva (DNA) for Future Biomedical Research for pediatric participants <18 years of age.		X												Collected from randomized participants who provided consent/assent for Future Biomedical Research (See Section 8.8).

^a When scheduling the Phone Contact (Day 15) and Visit 3 (Day 30), “Day 1” is the date of Visit 2 vaccination.
^b When scheduling the Phone Contact (Day 45) and Visit 4 (Day 60), “Day 1” is the date of Visit 3 vaccination.
^c When scheduling the Phone Contact (Day 75) and Visit 5 (Day 90), “Day 1” is the date of Visit 4 vaccination.
^d This Phone Contact (6 months after Visit 6) will only be conducted in recipients of V114 or Prevnar13™ at Visit 6.

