6.1 Study Intervention(s) Administered

The study interventions to be used in this study are outlined in [Table 1](#).

Table 1 Study Interventions

Arm Name	Arm Type	Intervention Name	Type	Dose Formulation	Unit Dose Strength	Dosage Level	Route of Admin	Vaccination Regimen	Use	IMP/NIMP	Sourcing
V114	Experimental	V114	Biological/Vaccine	Sterile suspension	Refer to IB	0.5 mL	IM	3 Doses: Visit 2 (Day 1) Visit 3 (Day 30) Visit 4 (Day 60)	Experimental	IMP	Central
		PNEUMOVAX™23 ^a OR	Biological/Vaccine	Sterile suspension	Refer to product labeling	0.5 mL	IM	Single Dose at Visit 6 (12 Months after Allo-HSCT)	Experimental	IMP	Central
		V114 (4 th Dose) ^b	Biological/Vaccine	Sterile suspension	Refer to IB	0.5 mL	IM	4th Dose at Visit 6 (12 Months after Allo-HSCT)	Experimental	IMP	Central
Pevnar 13™	Active Comparator	Pevnar 13™	Biological/Vaccine	Sterile suspension	Refer to product labeling	0.5 mL	IM	3 Doses: Visit 2 (Day 1) Visit 3 (Day 30) Visit 4 (Day 60)	Experimental	IMP	Central or local
		PNEUMOVAX™23 ^a OR	Biological/Vaccine	Sterile suspension	Refer to product labeling	0.5 mL	IM	Single Dose at Visit 6 (12 Months after Allo-HSCT)	Experimental	IMP	Central
		Pevnar 13™ (4 th Dose) ^b	Biological/Vaccine	Sterile suspension	Refer to product labeling	0.5 mL	IM	4th Dose at Visit 6 (12 Months after Allo-HSCT)	Experimental	IMP	Central

^a PNEUMOVAX™23 is administered to participants who do not have chronic graft-versus-host disease.

^b For participants with chronic graft-versus-host disease, a 4th dose of V114 or Pevnar 13™ (blinded; same as first 3 doses) is administered instead of PNEUMOVAX™23.

Admin = administration; IB = Investigator's Brochure; IM = intramuscular; IMP = investigational medicinal product; NIMP = non-investigational medicinal product.

The definition of IMP and NIMP is based on guidance issued by the European Commission. Regional and/or country differences of the definition of IMP/NIMP may exist. In these circumstances, local legislation is followed.

All supplies indicated in [Table 1](#) will be provided per the "Sourcing" column depending upon local country operational requirements. Every attempt should be made to source these supplies from a single lot/batch number. The study site is responsible for recording the lot number, manufacturer, and expiry date for any locally purchased product per local guidelines unless otherwise instructed by the Sponsor.

Refer to Section 8.1.8 for details regarding administration of the study intervention.

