8.1.8 Study Intervention Administration

V114 or Pevnar 13™ will be administered at Visit 2 (Day 1), Visit 3 (Day 30), and Visit 4 (Day 60). PNEUMOVAX™23, or alternatively V114 or Pevnar 13™ for participants with chronic GVHD, will be administered at Visit 6 (12 months after allo-HSCT).

Unblinded study personnel not otherwise involved in the conduct of the study will prepare and administer the study vaccine. Study vaccines should be prepared and administered by appropriately qualified members of the study personnel (eg, physician, nurse, physician's assistant, nurse practitioner, pharmacist or medical assistant) as allowed by local/state, country and institutional guidance. Procedures for handling, preparing, and administering the unblinded vaccines are provided in the Investigator Trial File Binder. Unblinded study personnel should follow the preparation and administration instructions for Pevnar 13™ as specified in the product labels.

Study vaccines should be removed from the refrigerator no more than 1 hour before vaccination. The time of removal and time of vaccination should be documented in the participant's chart.

If the V114 is provided as a syringe: Prior to administration of study vaccine, the unblinded pharmacist should shake vigorously to obtain a homogenous white suspension. If white-colored insoluble particle appears, the unblinded pharmacist should use rapid, horizontal hand-shaking for 5 to 10 seconds while holding the syringe in between the thumb and index finger until complete resuspension. This action should be repeated, as necessary. If appearance is otherwise, the vaccine should not be administered.

If V114 is provided as a vial: Prior to administration of study vaccine, the unblinded pharmacist should use rapid, horizontal hand-shaking for up to 5 seconds while holding the vial in between the thumb and index finger to obtain a homogenous white suspension. This action should be repeated, as necessary. If appearance is otherwise, the vaccine should not be administered.

The vaccine should not be used if the vaccine cannot be resuspended. Study personnel should follow the preparation and administration instructions for Prevnar 13™ and PNEUMOVAX™23 as specified in the product labels. Prevnar 13™ and PNEUMOVAX™23 will be supplied as a pre-filled syringe.

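### Does the varying chronic GVHD wording leave the Visit 6 vaccine rule and its safety groups undefined?

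*Combined protocol and SAP*

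**What the plan says.** Two sections describe the Visit 6 choice by onset. Section 4.1 states that "participants who develop chronic GVHD during the first year after allo-HSCT will be considered ineligible to receive PNEUMOVAX™23" and assigns them a 4th dose of blinded vaccine. Section 2.3 states that "participants who develop chronic GVHD during their first year after allo-HSCT will be considered ineligible to receive PNEUMOVAX™23", and its next sentence continues that "participants with chronic GVHD will receive a 4th dose of blinded study vaccine".

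Other places use a have/with form. Table 1, footnote a, reads "PNEUMOVAX™23 is administered to participants who do not have chronic graft-versus-host disease", and the synopsis has the same footnote. Footnote b of the synopsis table begins "For participants who have chronic graft-versus-host disease". Section 8.1.8 has the alternative vaccine "for participants with chronic GVHD, will be administered at Visit 6 (12 months after allo-HSCT"). Sections 2.1, 4.2, 4.3 and 8.1.12 and the exploratory objective in Section 3 are worded similarly.

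The two secondary safety objectives on the Visit 6 vaccinations (synopsis and Section 3) refer to participants who do or do not develop GVHD, without the word chronic.

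The Visit 6 window is "Day 335 to Day 395 after Allo-HSCT". The telephone contact six months later "will only be conducted in recipients of V114 or Prevnar13™ at Visit 6".

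**The concern.** Onset during a period and presence of a condition are different criteria. A participant whose chronic GVHD began in the first year and then resolved meets the first. The same participant fails the second if presence is judged at Visit 6. Two sites reading different sections could then give such a participant different vaccines. Follow-up would differ too, because only recipients of a 4th conjugate dose get the six-month call. The Visit 6 window also runs past one year, so onset late in the window might fall outside the first-year wording yet inside the other.

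The objectives raise a separate worry. Exclusion criterion 5 bars only Grade 3 or 4 GVHD, so participants with milder GVHD can enrol. A PNEUMOVAX 23 recipient who had only acute GVHD is outside the population named in that objective but would be summarized under it.

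**Working it through.** The documents give no figure to reproduce. The check sets the sections side by side, with a few day counts.

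**1. Do the two forms conflict?**

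| Place | Form | Time at which GVHD is judged |
|---|---|---|
| 2.3 (first sentence), 4.1 | develops in the first year | the first year |
| 2.3 (next sentence) | with | none stated |
| Synopsis and Table 1 footnotes | have / do not have | none stated |
| 8.1.8 | with | none stated; Visit 6 dates the injection |
| 2.1, 4.2, 4.3, 8.1.12, exploratory objective | with / without | none stated |

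The first-year form appears in 2 sections and the have/with form in 9 places, with Section 2.3 in both counts. Nowhere in the readable text does the have/with form say that the disease must be present at Visit 6. In Section 2.3 the have/with sentence directly follows the onset sentence and says what the group just named will receive. There the shorter form works as shorthand. A conflict over resolved disease needs a time of assessment that the reader has to supply.

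**2. Late onset.** Taking the first year to end on Day 365 (an assumption), the days of the Visit 6 window beyond it number 395 − 365 = 30 (Day 366 to Day 395), out of 395 − 335 + 1 = 61. Onset must fall in those 30 days and also precede a late Visit 6. The schedule labels the whole window as 12 months after transplant. If the first year is taken to run to that visit, the case vanishes.

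**3. Follow-up.** Visit 7 is 30 to 44 days after Visit 6 and the later call is 166 to 194 days after it. The gap between last contacts is 166 − 44 = 122 days at the shortest and 194 − 30 = 164 days at the longest. This is the planned difference between the two vaccines. It is not the size of an error. The vaccine-related SAE windows cannot be added as a further consequence. Section 3 gives 1 month after PNEUMOVAX 23 and 6 months after a 4th dose, but Sections 9.1 and 9.6.2 run to Month 13 for both. That is a separate inconsistency.

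**4. Effect on the analysis.**
- Section 9.5.2 groups safety data by the vaccine actually received. Section 9.6.2 sets its summaries by which vaccine was given at Month 12. GVHD status does not enter either definition, so inserting or omitting chronic in the objectives changes 0 proportions.
- Section 9.4.1 likewise defines the exploratory post-Visit 6 immunogenicity endpoints by the vaccine given.
- The primary IgG endpoint is at Day 90 and the primary safety summaries stop before the Visit 6 vaccination.
- Investigators are blinded to V114 versus Prevnar 13 (Section 6.3.3), so how a site reads the rule for a given clinical history cannot depend on the randomized arm.
- Section 9.3 plans estimation only, with no hypothesis test at Visit 6 or elsewhere.

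**5. Could GVHD history be reconstructed?** Section 4.1 records new onset or change in GVHD, and change, read literally, includes resolution. Section 8.4.8 is narrower (new onset or worsening since Day 1). Medical history before Day 1 (8.1.4) and follow-up of adverse events to resolution (8.4.3) may supply the rest, though neither names chronic GVHD.

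**The case for a change.** The strongest case for acting is that this rule decides which vaccine every participant reaching Visit 6 receives. Even if the two forms are equivalent, the text does not say whether both mean ever in the first year or present at the visit. Section 2.1 names diagnostic criteria (NIH consensus) but no time of assessment. The intervention tables and the administration section carry only the have/with form, so sites working from those could act differently from sites working from Section 4.1. A sentence of wording is cheap, and Amendment 04 already clarified GVHD wording elsewhere.

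Part of this stands. The readable text gives no explicit handling of chronic GVHD that has resolved, and the objectives do omit a word that the exploratory objective on the same vaccinations includes. It does not establish that the sections prescribe different vaccines, since that needs an added assumption about timing. Nor does it show an effect on any result. Figure 1 and the schedule comment for the Visit 6 vaccination could not be read here and may state the time, so its absence from the plan is not shown.

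**Conclusion.** The wording varies, but this does not call for a change to the plan. The dosing part is an unstated time of assessment, which those running the study can settle by confirming what the forms mean. The missing word in the two objectives is a clerical slip, and the exploratory objective and the dosing sections show what was meant. If the text is reissued, reconciling these passages is housekeeping. The sponsor decides what the clinical rule is, and no view on it is taken here.

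The omission changes 0 computed proportions. The late-onset case covers at most 30 days of onset dates under a Day 365 cut-off, and none if the first year runs to Visit 6. The number with resolved chronic GVHD is unknown, because the documents give no frequency, onset time or resolution rate. For any such participant, the vaccine and the length of follow-up could depend on how the site reads the rule.

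The conclusion rests on Section 2.3 using the two forms as one rule, and on the safety summaries being built by vaccine received as Sections 9.5.2 and 9.6.2 state. It would need another look if Figure 1 or the schedule comment gave a time of assessment that contradicts Section 4.1.
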